10.4.2 SENSITIVITY ANALYSIS

A tipping-point analysis will be performed for the primary effectiveness endpoint. Let n and m be the number of OMNI and [REDACTED] subjects that do not have the 12-month washed out DIOP due to any reasons other than the first four criteria listed in Section 10.4.1. The tipping-point analysis for Hypothesis I in Section [10.1](#) will be performed as follows:

Let X_{02} be the sample mean of the unmedicated DIOP change from baseline at 12 months for all OMNI (transluminal viscoelastic delivery AND trabeculotomy) subjects except for the n subjects and let X_i be that of the [REDACTED] excluding the m subjects. Let ω and ν be the worst and best unmedicated DIOP change from baseline at 12 months observed from the subjects. The increment of 0.05 mmHg will be used in the tipping-point analysis. The first iteration in the tipping point analysis is to use X_{02} to impute the missing values for the n subjects, use X_i to impute the missing values for the m subjects, and calculate the p-value of the statistical test described in Section [10.4.1](#). The second iteration is to use $X_{02} + 0.05$ (i.e., worse than X_{02}) to impute the missing values for the n subjects and $X_i - 0.05$ (i.e., better than X_i) to impute the missing values for the m subjects. The i th iteration is to use $X_{02} + 0.05 \times i$ to impute the missing values for the n subjects and $X_i - 0.05 \times i$ to impute the missing values for the m subjects. The iterations will stop when the p-value becomes insignificant or the imputed value for the OMNI (transluminal viscoelastic delivery AND trabeculotomy) group is worse than the ω value or the imputation for the [REDACTED] is better than the ν value, which comes first. A figure of p-value as the Y-axis and iteration as the X-axis will be provided.

The same tipping point analysis will also be performed for Hypothesis II in Section [10.1](#).

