10 STATISTICAL CONSIDERATIONS

10.1 SAMPLE SIZE CALCULATION

The sample size calculation is based on the primary effectiveness endpoint, mean change in unmedicated DIOP from baseline at the 12-month postoperative examination. The study goal is to determine, in reducing the IOP in eyes with OAG undergoing cataract extraction, either OMNI (ab-interno transluminal viscoelastic delivery AND trabeculotomy) is superior [REDACTED], or OMNI (ab-interno transluminal viscoelastic delivery alone) is not inferior to the [REDACTED] in lowering the IOP with a non-inferiority margin of 1.5 mmHg. Due to the multiplicity, the significance level is adjusted to a two-sided significance level of 0.025 for each of the two hypotheses. The statistical hypotheses for the primary effectiveness endpoint are as follows:

Hypothesis I:

$H_0: \mu_{02} = \mu_i$ versus $H_a: \mu_{02} < \mu_i$, where μ_{02} and μ_i are the mean change in unmedicated DIOP from baseline at the 12-month postoperative examination for the OMNI (ab-interno transluminal viscoelastic delivery AND trabeculotomy) and [REDACTED] groups, respectively. A negative mean change represents a mean reduction. The alternative hypothesis ($H_a: \mu_{02} < \mu_i$) is to prove that the mean change in unmedicated DIOP of the OMNI (ab-interno transluminal viscoelastic delivery AND trabeculotomy) group is lower than that of the iStent inject group. In other words, the OMNI (ab-interno transluminal viscoelastic delivery AND trabeculotomy) is superior to the [REDACTED] group in lowering the IOP.

Hypothesis II:

$H_0: \mu_{01} - \mu_i \leq -1.5 \text{ mmHg}$ versus $H_a: \mu_{01} - \mu_i > -1.5 \text{ mmHg}$, where μ_{01} and μ_i are the mean change in unmedicated DIOP from baseline at the 12-month postoperative examination for the OMNI (ab-interno transluminal viscoelastic delivery alone) and [REDACTED] respectively. Since negative μ_{01} and μ_i represent decreases in IOP, the alternative hypothesis ($H_a: \mu_{01} - \mu_i > -1.5 \text{ mmHg}$) is to prove that the mean change in unmedicated DIOP of the OMNI (ab-interno transluminal viscoelastic delivery alone) group is not worse than that of the [REDACTED] by 1.5 mmHg. In other words, the OMNI (ab-interno transluminal viscoelastic delivery alone) is not inferior to the [REDACTED] in lowering the IOP with a non-inferiority margin of 1.5 mmHg.

[REDACTED]

[REDACTED]

[REDACTED]

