10.4.1 PRIMARY EFFECTIVENESS ENDPOINT

The primary analysis of the primary effectiveness endpoint will be based on the AT population. The Baseline unmedicated DIOP will be used to impute the 12-month unmedicated DIOP for the subjects meeting any of the following criteria:

- Ocular hypotensive medications cannot be washed out properly at 12 months due to safety reasons.
- Have secondary surgical interventions (such as laser procedure or MIGS) to control IOP before the 12-month washout.
- Have any ocular procedures that can affect the IOP before the 12-month washout.

- Have IOP below 6 mmHg at 1 month or later
- Do not have the 12-month washed out DIOP due to any other reasons.

The change in unmedicated DIOP from baseline at 12 months will be calculated for each study eye as change = (12-month unmedicated DIOP – Baseline unmedicated DIOP).

The descriptive statistics (such as mean, standard deviation, median, minimum, and maximum) of the medication-free mean diurnal IOP and the change from baseline and the 95% confidence interval of the mean will be calculated for each of the three study groups. A two-sample t-test with a one-sided significance level of 0.025 will be used to compare the mean unmedicated DIOP change from baseline at 12 months for Hypotheses I and II described in Section [10.1](#). The two-sided 95% confidence interval based on the t-distribution will also be provided for the mean difference. In order to assess the pattern of the distribution, box-plots will be prepared for the medication-free mean diurnal IOP and its change from baseline for each of the three study groups.

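### The tipping-point analysis fills the shifted missing eyes with one constant per arm and runs the ordinary t-test, so at and near zero shift its standard error is too small, and robustness is overstated for borderline results

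*Combined protocol and SAP*

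**What the plan says.** Section 10.4.2 restricts the procedure to the n OMNI and m comparator eyes without a 12-month washed-out DIOP "due to any reasons other than the first four criteria listed in Section 10.4.1". That is the last criterion in Section 10.4.1: "Do not have the 12-month washed out DIOP due to any other reasons". Eyes under the first four criteria keep the baseline value, so their change is zero throughout.

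The step size is given first: "The increment of 0.05 mmHg will be used in the tipping-point analysis". The operative instruction follows it. Iteration one fills the n OMNI eyes with the OMNI arm mean `X_02`, and for the comparator the plan says to "use X_i to impute the missing values for the m subjects, and calculate the p-value of the statistical test described in Section" 10.4.1. Later iterations add a multiple of 0.05 to the OMNI constant and subtract the same multiple from the comparator constant. "The iterations will stop when the p-value becomes insignificant", or when the imputed value passes the worst or best observed change. The same analysis is repeated for Hypothesis II.

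The test in Section 10.4.1 is the ordinary one: "A two-sample t-test with a one-sided significance level of 0.025 will be used". The visible text has no multiple imputation, no residual draw, and no correction to the variance or degrees of freedom.

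**The concern.** A block of identical imputed values at the arm mean adds nothing to the sum of squares, yet each value counts in full in the sample size. The t-test therefore sees more information than was collected, and its p-value is too small. This is the only analysis under the sensitivity heading for the primary endpoint, and it serves both the superiority and the non-inferiority claim. Its outputs are a p-value curve and the step at which significance is lost, which are the quantities affected. A stress test that errs towards declaring robustness can report that a result survives shifts at which a correct analysis has already lost significance.

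**Working it through.** **Inputs.** The Synopsis and Section 5 give 459 randomised 1:1:1; the Synopsis gives 411 completers and about 10% dropout. SD, effect size and power are not visible, so SD 3.5 to 5 mmHg and an observed benefit of 1.25 to 2.0 mmHg are assumed. The standard-error ratio at zero shift depends on neither.

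**The plan's own figure.** 411/3 = 137 completers per arm; 137/0.90 = 152.2, rounded up to 153; 3 × 153 = 459, as stated. If all planned dropout fell into n and m, 153 − 137 = 16 eyes per arm (10.5%) would be filled.

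**Formulas, per arm.** N = 153 eyes, k filled, r = N − k not filled (including those fixed at zero change), SD s among the r, shift d.

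- Constant fill: variance of the arm mean = [(r−1)s² + (rk/N)d²] / [N(N−1)].
- Benchmark A, delta-adjusted multiple imputation with Rubin's rules and many imputations: s²/r + (rk/N)d² / [N(N−1)].
- Benchmark B, non-missing eyes only with the missing fraction treated as fixed: s²/r.

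**Zero shift.** A and B coincide. The ratio of constant-fill to correct standard error is √[r(r−1)/(N(N−1))]. For k = 16 this is √[(137 × 136)/(153 × 152)] = √0.801 = 0.895. The true one-sided level is P(Z > z × ratio), for example P(Z > 1.96 × 0.895) = 0.040.

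| Filled per arm | SE ratio | Nominal 0.025 acts as | Nominal 0.0125 acts as |
|---|---|---|---|
| 4 (2.6%) | 0.974 | 0.028 | 0.0145 |
| 8 (5.2%) | 0.948 | 0.032 | 0.017 |
| 16 (10.5%) | 0.895 | 0.040 | 0.022 |

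A simulation of 40,000 runs with 16 filled gave 0.0393 for the constant fill and 0.0245 for the available-case test. Both nominal levels are shown because Section 10.1 says that "the significance level is adjusted to a two-sided significance level of 0.025 for each of the two hypotheses" (one-sided 0.0125), while Section 10.4.1 uses one-sided 0.025. The stopping rule therefore has no single threshold.

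**Larger shifts.** The d² term adds spread to the filled data. Against A with 16 filled, the ratio is 0.895, 0.904 and 0.923 at shifts of 0, 1 and 2 SD. Against B it reaches 1 where (r−1)s² + (rk/N)d² = s²N(N−1)/r. For k = 16, d²/s² = (169.75 − 136)/14.33 = 2.36, so d = 1.54 SD. For 8 and 4 filled the crossing is at 1.47 and 1.44 SD.

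**Tipping shift, SD 4, benefit 1.5, 16 filled, one-sided 0.025.** The mean difference at shift d is −1.5 + 2(16/153)d.

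- Constant fill at d = 3.00: difference −0.873; SE = √{2 × [136 × 16 + 14.33 × 9]/23256} = 0.445; p = 0.025, the first step above the threshold.
- Benchmark A at d = 2.55: difference −0.967; SE = √{2 × [16/137 + 14.33 × 6.50/23256]} = 0.492; p = 0.025, the first step above.
- An explicit multiple-imputation run (1,500 imputations) gave p = 0.039 at d = 3.00.

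Other assumed cases with 16 filled, in mmHg per arm at one-sided 0.025:

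| SD | Benefit | Constant fill | A | B |
|---|---|---|---|---|
| 5 | 1.25 | 0.90 | 0.30 | 0.30 |
| 4 | 1.5 | 3.00 | 2.55 | 2.65 |
| 3.5 | 2.0 | 5.60 | 5.25 | 5.60 |

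Over 18 scenarios (SD 3.5, 4, 5; benefit 1.25, 1.5, 2.0; level 0.025 or 0.0125) the constant fill tipped later than A by 0.2 to 0.65 mmHg, or 4 to 13 steps. Against B it tipped at the same step or up to 0.65 mmHg later. For Hypothesis II the same variance formulas apply, with the distance from the observed difference to the 1.5 mmHg margin in place of the benefit.

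**The case against.** A reader might infer that every p-value on the plotted curve is too small. The plan does not support that on every valid benchmark. Against Rubin's variance the shortfall persists over the shifts checked (0 to 2 SD). Against a standard error from the non-missing eyes it closes near 1.5 SD and then reverses. With 4 filled per arm, SD 4 and benefit 1.5, the constant fill tips at 10.30 mmHg and benchmark B at 11.25, so there the planned method understates robustness. The worst/best-value limit may stop the iterations before that.

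A reader might also infer that every missing eye is affected, or that 16 per arm is the expected number. Neither follows. Eyes under the first four criteria are never shifted. Section 8.10 withdraws subjects after a secondary IOP-lowering procedure, but they meet the second criterion and so fall outside n and m. Section 8.7 exits eyes with complicated cataract surgery, and the analysis set is As Treated, so neither 153 nor 10% carries over exactly. With 4 filled per arm the shortfall is under 3%.

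Finally, the analysis is supportive, no pass/fail tipping value is set, and Section 10.4.4 offers a related exploratory comparison of percent change on available data. This limits the consequence. It does not make the standard error right where the shift is small.

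**Conclusion.** The point holds with limits. The plan's wording makes the standard error too small at and near zero shift, by about the fraction of eyes filled: under 3% with 4 per arm and 10.5% with 16, the latter only if all planned dropout falls in n and m. That part rests on algebra and 153 eyes per arm, not on the hidden planning inputs.

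The tipping shifts do rest on assumed SD and benefit. Robustness is clearly overstated when the result is near the threshold or the missing fraction is larger: 0.90 against 0.30 mmHg in the most sensitive tabulated case. For strong results with few missing eyes, the size and even the direction depend on the benchmark. The primary p-value does not come from this procedure and is unaffected. Because this is the only named sensitivity analysis and the repair is cheap, it should be corrected before the 12-month data are analysed.

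**What to change.** In Section 10.4.2, for both hypotheses, replace the constant fill plus ordinary t-test with one of these:

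1. Delta-adjusted multiple imputation. Draw the missing changes from the distribution of the same eyes that define `X_02` and `X_i`, add the shift to the OMNI draws and subtract it from the comparator draws, and pool by Rubin's rules. Fix the seed, and use enough imputations to resolve 0.05 mmHg steps.
2. A test of the shifted mean difference with standard error and degrees of freedom taken from the non-missing eyes only. This is simpler and has no simulation noise.

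The stopping limit must be adapted, because multiple imputation has no single imputed value to compare with the worst and best observed changes. Apply the limit to the shifted arm means (`X_02` plus shift, `X_i` minus shift), not to individual draws. Keep the p-value plot. State the significance threshold that ends the iterations. Index the shift as 0.05 × (i − 1): the text uses 0.05 at the second iteration but 0.05 × i at the i-th.

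The cost is SAP wording and modest programming, with no new data. The reported tipping point will usually be slightly less favourable when the result is near the threshold.

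### The tipping-point analysis in 10.4.2 never evaluates the primary's zero-change scenario or unequal departures by arm, so its tipping shift is not a distance from the primary result

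*Combined protocol and SAP*

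**What the plan says.** Section 10.4.1 fixes the primary imputation: "The Baseline unmedicated DIOP will be used to impute the 12-month unmedicated DIOP for the subjects meeting any of the following criteria". The fifth criterion is the catch-all: "Do not have the 12-month washed out DIOP due to any other reasons". Setting the 12-month value to baseline makes the change exactly zero for every such eye, in every arm.

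Section 10.4.2 defines n (OMNI) and m (comparator) as the "subjects that do not have the 12-month washed out DIOP due to any reasons other than the first four criteria listed in Section 10.4.1". These are the fifth-criterion eyes. Eyes under criteria 1 to 4 keep their zero change and sit inside the arm means X_02 and X_i. On the start: "The first iteration in the tipping point analysis is to use" X_02 for the n eyes and X_i for the m eyes ("to impute the missing values for the n subjects, use X_i to impute the missing values for the m subjects"). On the step size: "The increment of 0.05 mmHg will be used in the tipping-point analysis". At each step the OMNI value gets worse and the comparator value better by the same amount. On stopping: "The iterations will stop when the p-value becomes insignificant", or when an imputed value passes the worst or best observed change. The output is a plot of p-value against iteration number. The same procedure is to be applied to Hypothesis II.

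No other sensitivity analysis of the primary endpoint is committed to. Section 10.2.2 says only that ITT analyses may be performed if needed.

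**The concern.** A tipping-point analysis should show how far the missing-data assumption can move before the primary conclusion changes. Here the primary assumption is zero change, but the analysis starts from a different one and follows a single line away from it. Two questions are left unanswered: where the primary result lies among the scenarios examined, and what happens if the missing eyes of one arm depart more than those of the other.

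For a superiority test the two anchors can give quite different answers. Arm-mean imputation keeps the full observed difference and adds no spread. Zero-change imputation with similar missingness dilutes the difference and widens the SD. The plot could then begin significant, and stay so for several steps, for a comparison that the primary test does not support.

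**Working it through.** **Inputs from the plan.** 459 randomized 1:1:1 (section 5), 411 completers and about 10% drop-out (synopsis). Check: 411/3 = 137 per arm; 137/0.9 = 152.2, rounded up to 153; 3 x 153 = 459, as stated. That leaves 153 - 137 = 16 missing per arm. The test is the two-sample t-test at one-sided 0.025 (10.4.1).

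**Assumed.** All 153 per arm are in the AT population, all missing eyes fall under the fifth criterion, and none meets criteria 1 to 4. The planned means and SD are not readable, so ranges are used.

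**Step 1: can the path pass through the primary scenario?** The path visits the pairs (X_02 + d, X_i - d), whose sum is always X_02 + X_i. The primary scenario is (0, 0), with sum 0. If both means are reductions the sum is negative, so the path never reaches it.

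**Step 2: formulas.** With 137 observed eyes at mean X and 16 imputed at v, the arm mean is (137X + 16v)/153. The arm's sum of squares is 136 x SD² + (137 x 16/153)(X - v)². Pool over 304 degrees of freedom; SE = s x sqrt(2/153).

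**Step 3: means -8.0 and -7.0, SD 4.**
- Primary (v = 0): difference (137/153)(-1.0) = -0.895. Sums of squares 2176 + 14.33 x 64 = 3093 and 2176 + 14.33 x 49 = 2878, so s = sqrt(5971/304) = 4.43, SE = 0.507, p = 0.039.
- Start (v = X): difference -1.0, s = sqrt(4352/304) = 3.78, SE = 0.433, p = 0.011.
- Observed eyes only: SE = 4 x sqrt(2/137) = 0.483, p = 0.020. The start's advantage is therefore not only the small SE that comes from imputing a constant.
- Path: the difference at shift d is -1.0 + 2(16/153)d. It equals the primary's difference at d = 0.50. Significance is lost at d = 0.75. The primary's p would be reached only at d = 1.15, after the path has stopped.

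**Step 4: other means, 16 missing per arm, SD 4.** Tip is the shift in mmHg per arm at which p first exceeds 0.025.

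| Means | Primary p | Start p | Tip, planned path | Tip, lockstep from (0, 0) | Tip, OMNI alone from arm means |
|---|---|---|---|---|---|
| -8.0, -7.0 | 0.039 | 0.011 | 0.75 | already non-significant | 1.40 |
| -8.0, -6.8 | 0.017 | 0.003 | 1.65 | 0.40 | 3.20 |
| -8.5, -7.0 | 0.0046 | 0.0003 | 3.00 | 1.60 | 5.80 |

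Over 27 settings (SD 3.5 to 4.5, comparator mean -5 to -9, difference -1.0 to -1.5, 16 missing per arm) the start favoured OMNI more than the primary did, in both difference and p.

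**Step 5: unequal missingness.** With 153 per arm, the start difference minus the primary difference is (n X_02 - m X_i)/153. It changes sign when m/n exceeds X_02/X_i. For means -8.0 and -6.8, SD 4:

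| n OMNI, m comparator | Primary p | Start p | Tip, planned path |
|---|---|---|---|
| 20, 12 | 0.088 | 0.003 | 1.65 |
| 16, 16 | 0.017 | 0.003 | 1.65 |
| 12, 20 | 0.0019 | 0.0029 | 1.65 |
| 10, 22 | 0.0005 | 0.0029 | 1.65 |

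The primary p runs from 0.088 to 0.0005 while the reported tipping shift does not move.

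**Step 6: index.** The first iteration adds 0 and the second adds 0.05, but the general term adds 0.05 x i, which is 0.10 at i = 2. The plot's axis is the iteration number, so the mmHg value of each point is ambiguous by one step.

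**The case against.** The strongest reply is that the anchor is a disclosed design choice. Start, step, stopping rule and plot are all stated, the plan never calls the iteration count a distance from the primary, and a reader who has the primary p-value can look for that height on the plot. The primary inference remains the 10.4.1 test, so a significant start beside a non-significant primary is no false claim of success; it would show that the conclusion depends on zero-change imputation. This stands as far as it goes. It does not supply the missing scenarios, and in the -8.0 versus -7.0 case the path stops before it reaches the primary's p.

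A reader might infer more: that the analysis generally overstates the robustness of Hypothesis I, or that moving the arms together is lenient. The documents do not support either. The direction depends on n, m and the means, and reverses with enough extra comparator loss (step 5). Lockstep is harsher per mmHg than moving OMNI alone (1.65 against 3.20).

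Nor should the gap between the planned tip and the point where the path regains the primary's p be generalised. For -8.0 versus -6.8 that point is 1.35 of 1.65 mmHg, but the case sits near the threshold and includes the SE effect: with the observed-eyes SE the figures are 0.85 and 1.20. For -8.5 versus -7.0 they are 1.70 of 3.00.

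**Conclusion.** The point holds as one of anchor and coverage. The path excludes the primary's own scenario whenever both arms show a mean reduction, and it excludes every unequal departure by arm. That follows from the text and needs no assumed figures. For Hypothesis I, with OMNI ahead and missingness similar or heavier in OMNI, the path starts on the OMNI-favourable side of the primary and can be significant when the primary is not (0.011 against 0.039 in the illustration).

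All p-values and shifts rest on the assumed means and SD, on 16 missing eyes per arm except where varied, and on one-sided 0.025. Section 10.1 sets a stricter level, which would move the tipping points but not the argument. The coverage gap applies to Hypothesis II as well; no direction is claimed there. The primary test is unaffected. This is a worthwhile, inexpensive improvement to the sensitivity analysis.

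**What to change.** In 10.4.2, replace or supplement the single path with a two-way grid. Give the missing eyes of each arm a value independently, over the range from best to worst observed change, and run the 10.4.1 test at each grid point, for both hypotheses. Mark the (0, 0) primary scenario and the (arm mean, arm mean) scenario. Report the boundary where the conclusion changes and where it lies relative to the primary scenario. If the path figure is kept, label its axis with the actual shift in mmHg, 0.05 x (i - 1), and correct the general term to match.

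The cost is SAP wording and a short program, with no new data or visits. The downside is that the stated robustness may look smaller than on the planned plot.

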10.4.3 COVARIATE ANALYSIS

The following variables will be examined for their prognostic value to the primary effectiveness endpoint using the AT population with the imputation used for the primary analyses:

- Age group (based on observed quartiles)
- Gender (male and female)
- Race/ethnicity
- Baseline unmedicated DIOP group (based on observed quartiles)
- Number of ocular hypotensive medications at screening
- Study Site

For the primary effectiveness endpoint, two-way ANOVA with study group (three groups), one of the factors listed above, and the interaction between the study group and the factor will be used to check the possible covariate effects. A p-value of 0.15 will be used for evaluating the possible covariate effects. It should be noted that the subgroups of these covariates will be re-examined and may be re-categorized or eliminated due to small sample size (if there are < 10 subjects within each subgroup).

The scatter plots of the 12-month unmedicated DIOP versus the baseline unmedicated DIOP along with a 45° line will be provided. The scatter plot of the percent change in unmedicated DIOP from baseline to 12 months versus the baseline unmedicated DIOP will also be provided. The Box plots of the change and percent change in unmedicated DIOP from baseline to 12 months will be prepared for each category of the covariates (except for the study site).

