10.3 DEMOGRAPHICS AND BASELINE CHARACTERISTICS

Subject demographics (age, race/ethnicity and gender) will be summarized by study group for the ITT, AT, and Safety populations using descriptive statistics. Age will be summarized as a continuous variable and categorized into the four groups based on the observed quartiles.

The baseline medicated IOP and washout (unmedicated) IOP will be summarized by study groups for the ITT and AT populations. They will be treated as continuous variables. The number of glaucoma medications in use at enrollment will be prepared for each of the study groups using descriptive statistics for categorical variables.

Medical and Ocular history will be summarized for each study group by number and percentage of subjects in the ITT and AT population.

For the Safety Population, ITT, and AT populations, subject accountability will be prepared based on Table G.1 of ANSI Z80.27-2014.

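### Section 10.4.3 tests age and baseline unmedicated DIOP only as quartile groups; adding a continuous model beside them would give a more sensitive trend and interaction test from data already collected

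*Combined protocol and SAP*

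**What the plan says.** Section 10.4.3 (Covariate Analysis) names six factors to be examined for prognostic value to the primary endpoint in the AT population. Two of them are continuous measurements that are grouped before use: "Age group (based on observed quartiles" and "Baseline unmedicated DIOP group (based on observed quartiles". Each factor is examined in a "two-way ANOVA with study group (three groups), one of the factors listed above, and the interaction between the study group and the factor". The threshold is liberal: "A p-value of 0.15 will be used for evaluating the possible covariate effects". Subgroups "may be re-categorized or eliminated due to small sample size (if there are < 10 subjects within each subgroup".

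Both variables also appear ungrouped, but not in a test. Section 10.3 says "Age will be summarized as a continuous variable and categorized into the four groups based on the observed quartiles", which is descriptive. Section 10.4.3 adds graphs for baseline pressure: "The scatter plots of the 12-month unmedicated DIOP versus the baseline unmedicated DIOP along with a 45° line will be provided", with a second scatter plot for percent change. There is no such plot for age.

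The primary analysis in 10.4.1 has no covariates: "A two-sample t-test with a one-sided significance level of 0.025 will be used" for each hypothesis. Sections 10.4.4 and 10.4.5 contain no test of interaction with age or baseline DIOP.

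**The concern.** Section 10.4.3 is the only place in the visible text where the plan tests whether the difference between an OMNI arm and the comparator changes with baseline pressure or age. Grouping a continuous covariate into quartiles has two costs. Variation within each quartile is discarded, and the test is spread over more degrees of freedom, so a steady trend is harder to detect. A screening level of 0.15 suggests that the screen is meant to be sensitive, and the coding works against that. The quartile model also gives no estimate of the treatment difference at a chosen baseline DIOP, only contrasts between groups whose limits are unknown until the data are in.

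**Working it through.** **The plan's own figure.** The plan states no power for the covariate tests, so only the sample size can be reproduced. The Synopsis gives 411 completing, about 10% drop-out and 1:1:1 allocation. 411/3 = 137 per arm; 137/0.90 = 152.2, rounded up to 153; 153 × 3 = 459, as stated. I use N = 411 below; N = 459 gives the same powers to within 0.1 percentage point.

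**Degrees of freedom per covariate, three groups.**
- Quartiles: main effect 4 − 1 = 3; interaction (3 − 1)(4 − 1) = 6; total 9. Residual 411 − 12 = 399.
- Linear term: main effect 1; interaction (3 − 1) × 1 = 2; total 3. Residual 411 − 6 = 405.

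The 6 residual degrees of freedom saved, out of about 400, are immaterial. What matters is the numerator.

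**Information kept by quartiles.** This is the between-quartile variance divided by the total variance. For a standard normal covariate the quartile means are ±1.271 and ±0.325, so the fraction is (1.271² + 0.325²)/2 = 0.861. The documents do not give the covariate distributions, so I took a range: about 94% for a uniform covariate, 87% for a normal truncated to the 24–39 mmHg entry range in the Synopsis, and 79% for a right-skewed covariate on that range.

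**Power at 0.15, linear effect, normal covariate.** Power = P(F′ > F critical), where F′ is noncentral F. The noncentrality is set so that the linear test has 80%, then multiplied by 0.861 for quartiles.

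| Test | Noncentrality for 80% | Linear | Variance loss only | Extra df only | Quartiles (both) |
|---|---|---|---|---|---|
| Interaction (2 vs 6 df) | 6.57 | 80% | 75% | 65% | 59% |
| Main effect (1 vs 3 df) | 5.22 | 80% | 75% | 66% | 61% |

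For the quartile interaction test to regain 80%, the sample would have to be about 1.7 times as large. Most of the loss comes from the numerator degrees of freedom, that is, from not assuming a shape.

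**Other effect sizes.** Partial R² values are assumed, with a normal covariate and a linear effect. Interaction power, linear against quartile, is 0.64 vs 0.44 at 1% and 0.88 vs 0.68 at 2%. Main-effect power is 0.72 vs 0.53 and 0.93 vs 0.78. Over partial R² of 0.5% to 3% and all four distributions, the gap is about 5 to 23 percentage points.

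**When the relation is not linear.** Simulation, N = 411, 1,500 runs per setting, standardized effect 0.12, normal covariate; power of linear term vs quartiles:

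| Shape | Main effect | Interaction |
|---|---|---|
| Middle quartiles differ from outer | 0.14 vs 0.74 | 0.14 vs 0.46 |
| Symmetric U | 0.15 vs 0.38 | 0.16 vs 0.27 |
| Top-quartile threshold | 0.65 vs 0.72 | 0.42 vs 0.45 |

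With a skewed covariate a quadratic shape favors the linear term (main effect 0.86 vs 0.51), so the direction depends on both shape and distribution. With no effect, both codings reject at 0.14 to 0.15, so the level is held.

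**A flexible continuous term.** A 3-df spline crossed with three groups uses 3 + 6 = 9 df, the same as quartiles. With no information lost, its interaction test at noncentrality 6.57 has about 65%, against 59% for quartiles.

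**The case against.** The case for leaving the section alone is reasonable. Quartile ANOVA assumes no shape, which is a legitimate property in a screen, and nothing in the documents says that the relation is linear. A reader might infer that continuous coding recovers the lost power for nothing. It does not: the move from 59% to 80% is mostly bought by assuming linearity, and a full spline gains about 6 points. That part of the objection stands, and it is why the quartile analysis should be kept.

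A reader might also infer that sample-dependent cut points make the results irreproducible. The documents do not support that. The rule, observed quartiles, is prespecified and can be applied to any data set; only the numerical limits will differ. It also balances group sizes, at about 411/12 ≈ 34 subjects per cell on average, so the rule for fewer than 10 subjects should rarely affect these two factors.

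Nor does the plan say that a non-significant interaction will be taken as evidence of consistency. Section 10.4.3 speaks only of prognostic value and possible covariate effects. The scatter plots would show a clear baseline trend, although they test nothing and do not cover age.

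What the objection does not answer is that the plan has no test aimed at a simple trend, which is a natural first form to look for with age or baseline pressure, and no estimate of the treatment difference at a given covariate value.

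**Conclusion.** The point holds in a limited form. Age and baseline DIOP are tested only as quartile groups, and under a roughly linear relation this costs about 20 percentage points of power at 0.15 (80% to 59% for the interaction, 80% to 61% for the main effect). Of that, about 5 points come from discarded variance acting alone; the remainder reflects the freedom from a shape assumption. These figures assume a normal covariate and an effect for which the linear test has 80% power; retained information is about 79% to 94% over the distributions considered. For a non-monotone relation the advantage can reverse.

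It would be wrong to infer that the primary conclusions are weakened. Both hypotheses are tested by an unadjusted t-test in 10.4.1, and the quartile coding does not enter it. This is a cheap improvement to a secondary screen.

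**What to change.** In 10.4.3, for age and for baseline unmedicated DIOP separately:

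1. Prespecify a linear model for the 12-month change with study group, the covariate as continuous, and their interaction, in the same AT population with the same imputation and at the same 0.15 level.
2. Prespecify one non-linearity check, for example added spline terms, and say what will be reported if it is positive.
3. Report each OMNI-minus-comparator difference with its confidence interval at covariate values stated in advance.
4. Keep the quartile ANOVA, tables and box plots beside this model.

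The cost is SAP wording and one more exploratory test per covariate; no added subjects, visits or measurements are needed. The continuous model carries a linearity assumption, which the check and the retained quartile analysis guard against. If a full 3-df spline with interaction is made the main continuous model, its test should not be expected to recover more than the within-quartile information.
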